3.9 Interim Analyses

No formal interim analyses were planned for Part C.

This document describes analyses to be included in the final CSR.

3.10 Multicenter Studies

A review of by-center effects will be performed in the context of data listing review. However, the sample size precludes formal assessment of by-center effects.

3.11 Multiple Comparison/Multiplicity

As this is an extension of an initial proof-of-concept study, no adjustment for multiple testing is planned.

3.12 Examination of Subgroups

The sample size in this study is not sufficient to allow rigorous assessment of outcomes by subgroups, and the study is not powered for subgroup assessment. However, exploratory assessments of the outcomes may be performed with a limited number of extrinsic or intrinsic factors, including age of the subject, location of the flare-up, amount of new HO, number of flare-up treatments, patients with extended flare-up dosing, or other variables as appropriate.

4 Analysis Populations

4.1 Enrolled Population

The Enrolled Population will include all subjects enrolled in Part C.

Unless stated, analysis for Enrolled Population will be presented by groups: PVO 20/10 mg Only, nonflare-up PVO 5 mg, PVO total, and Never Received PVO Treatment. The PVO 20/10 mg Only group only includes subjects who didn't take PVO 5 mg.

4.2 Treated Population

The Treated Population will include all subjects in the Enrolled Population who took at least one dose of palovarotene in Part C (either flare-up treatment or non-flare-up treatment).

The analysis for Treated Population will be presented by group combined PVO 20/10 mg in Part C, non-flare-up treatment PVO 5 mg and PVO Total.

The Treated Population will be the primary population for safety assessments.

4.3 Flare-up Treated Population

The Flare-up Treated Population will include all subjects in the Treated Population who took at least one dose of flare-up based treatment in Part C.

The analysis for Flare-up Treated Population will be presented by group: combined PVO 20/10 mg.

4.4 Flare-up Per Protocol Population

The Flare-up Per Protocol Population was to include all subjects in the Flare-up Treated Population with no major protocol deviations that may impact the efficacy assessment and who were at least 80% compliant with flare-up dosing.

Due to the small sample size, particularly when the additional restriction that baseline WBCT must be taken more than 30 days after the end of the previous flare-up (as was the case for Study 301 and NHS), formal per-protocol analyses are not planned to be performed.

4.5 Non-Flare-up Treated Population

The Non-Flare-up Treated Population includes all subjects in the Treated Population who took at least one dose of non-flare-up based treatment in Part C.

The analysis will be presented for subjects who took PVO non-flare-up based dosing with 5 mg (including weight-adjusted doses).

4.6 Restart Full Analysis Set

Restart Full Analysis Set (RFAS) includes all enrolled subjects in the Principal Enrolled Population (EP) who restarted palovarotene therapy after January 2020 and have at least two HO volume measurements in Part C trial on or after restart, with the first such WBCT imaged at least 30 days after the end of the previous flare-up.

4.7 Part D Analysis Set

Part D Population includes all skeletally immature subjects who stopped taking study medication for any reason before completion and had at least one follow-up visit following last dose. All analyses involving this population will be descriptive.

4.8 Pharmacokinetic Population

The Pharmacokinetic (PK) Population will include all subjects in the Treated Population who have at least one post-dose measurable concentration. The analysis will be presented for subjects who took non-flare-up based dosing of PVO 5 mg (including weight-adjusted) and/or flare-up based dosing of PVO 20/10 mg (including weight-adjusted doses).

5 Subject Data

5.1 Subject Disposition

Subjects disposition will be summarized for Enrolled Population:

- Number of subjects in each analysis population
- Number of subjects who discontinued treatment from Part C early and reasons for discontinuation
- Number of subjects who prematurely withdrew from Part C and reason for study discontinuation
- Number of subjects who completed Part C.
- Duration (months) of participation in Part C. This will be calculated as (date of completion of Part C/discontinuation - date of informed consent for Part C)/30.5.
- Number of subjects by following categories:
 - ≤6 months
 - >6 – 12 months
 - >12 – 18 months
 - >18 – 24 months
 - >24 months

Note: The total duration of participation in Part C and Part D, is a maximum of 4 years.

Subjects disposition will be summarized for Enrolled Population in Part D by listings.

–

5.2 Eligibility Criteria

Eligibility criteria (inclusion/exclusion) will be listed with any specific criteria that were not met shown in the by-subject listing for the Enrolled Population.

5.3 Protocol Deviations

Major protocol deviations will be identified prior to locking the database for Part C and may include, but are not limited to, departures from the inclusion/exclusion criteria, non-compliance with investigational product, use of restricted concomitant medications, and non-compliance with study procedures. Major protocol deviations will be summarized for the Enrolled Population.

For the NDA interim report, protocol deviations were not summarized, due to the study being ongoing at that time.

5.4 Demographic and Other Baseline Characteristics

Demographic and other baseline characteristics such as age, age group (6-15, 15+; 6-18, 18+), sex, race, ethnicity, height (cm), and weight (kg) will be summarized for all analysis populations.

5.5 Medical History

Medical history will not be collected as there are no new subjects in Part C. Subjects medical history was collected and summarized previously in Part A and Part B.

5.6 Prior and Concomitant Medications

Prior and concomitant medications will be coded using the WHO Drug Dictionary (March 2014).

- Prior medications are those the subject used prior to first dose of study drug. Prior medications can be discontinued before first dose of study drug or can be ongoing during the treatment phase.
- Concomitant medications are any treatments received by the subject after first dose of study drug, during Part C. Concomitant medications first received after first dose of study drug in Part C will also be referred to as new onset medications.
- New Onset medications are concomitant medications first received after the first dose of study drug

A given medication can be classified as a prior medication, or as a concomitant medication. Note that these categories are not mutually exclusive. A medication initiated prior to first dose of study drug and continued during the treatment-emergent period will be prior and concomitant.

The prior and new onset medications will be summarized based on the Enrolled Populations as follows:

- Prior medications discontinued prior to the first dose of study drug
- Prior medications ongoing at the first dose of study drug
- New onset medications during study
- Concomitant medications

Systemic glucocorticoids will be summarized including:

- Glucocorticoids taken for palovarotene treated flare-ups for Flare-up Treated population
- Glucocorticoids taken for condition aggravated adverse event for Enrolled Population
- Glucocorticoids taken for all other adverse event for Enrolled Population

The medications will be summarized according to the WHODrug Global March 2014 by Anatomic Therapeutic Class (ATC) and preferred term.. The ATC Class 3 name will be presented if available, and if not available the ATC class 2 name will be presented.

Systemic glucocorticoids used for flare-ups is defined as initiated 9 days prior to start of palovarotene for a flare-up cycle or within 9 days of flare-up cycle initiation which is categorized as a steroid used for treated flare-up or taken initially for a flare-up treated with palovarotene during a flare-up cycle.

For the purposes of analysis, incomplete medication start and stop dates will be imputed (See Section 3.7).

5.7 Treated Flare-ups Starting During Part C

Treated flare-ups for flare-up based treatment during Part C will be summarized for Flare-up Treated Population and Flare-up Per Protocol Population including following variables:

- Total number of flare-up cycles
- Number of flare-up cycles with dosing extended beyond 12 weeks
- Number of flare-up cycles for which an interruption of study drug occurred during flare-up dosing overall and by high or low flare-up based doing. Where an interruption includes ≥ 14 days without dosing.
- Number of flare-up cycles with dosing reductions overall and by high or low flare-up based doing
- Number of flare-up cycles for which study drug was discontinued during flare-up dosing overall and by high or low flare-up based doing
- Total number of treated flare-ups across all flare-up cycles
- Number of flare-ups treated per cycle
- Number of flare-ups treated per cycle categorized
 - 1 flare-up
 - 2 flare-ups
 - 3 flare-ups
 - 4 flare-ups
 - >5 flare-ups
- Number of intercurrent flare-ups treated per cycle
- Number of palovarotene treated trauma flare-ups

A dose interruption is defined as dosing interrupted for at least 14 days without dosing.

Number of subjects with treated flare-ups will also be summarized for Flare-up Treated Population including following variables:

- Number of subjects with treated flare-up cycles
- Number of subjects with treated flare-up cycles by categories
 - 1 flare-up cycle
 - 2 flare-up cycles
 - 3 flare-up cycles
 - 4 flare-up cycles
 - ≥ 5 flare-up cycles
- Number of subjects with flare-up cycle with dosing extended beyond 12 weeks
- Number of subjects for which an interruption of study drug occurred during flare-up cycle dosing overall and by high or low flare-up based doing
- Number of subjects for which study drug was discontinued during flare-up cycle dosing overall and by high or low flare-up based doing

- Number of subjects with dose reduction during flare-up cycle dosing overall and by high or low flare-up based dosing

Treated flare-up data as reported by the subject and by Investigator including symptoms, probable causes, and location(s) will be summarized for the Flare-up Treated Population.

Flare-up location mapping is described in [Table 11](#).

5.8 Annualized Flare-up Rate

Flare-ups are counted using the number of subject/Investigator-reported flare-ups (including intercurrent flare-ups). Rates will be calculated as the total number of flare-ups divided by duration of follow-up (year). The duration of follow-up (years) is defined as (last date on study – Part C Study Day 1 + 1)/365.25. Flare-up rate will be calculated separately for pre-interruption, during interruption, and after re-start of palovarotene dosing.

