Based on additional post-hoc analyses presented to the DMC on January 21, 2020, the DMC noted that using the square-root transformation of the data in the primary analysis appears to have moved the statistical conclusion from significant therapeutic benefit to showing futility of the treatment. The DMC also noted that the dilemma created by these highly disparate results precludes a confident conclusion about futility. As such, the DMC recommended that additional analyses be conducted and provided to them for consideration at the next interim analysis.

US FDA instituted a partial clinical hold on dosing of palovarotene due to premature physéal closure (PPC) for subjects <14 years of age on December 4, 2019; as of the finalization of this SAP amendment, dosing

has not yet resumed for these subjects. Dosing on all other subjects in Study 301 and Study 202 Part C not subject to US FDA's partial clinical hold was interrupted following the January 21, 2020 DMC meeting while the protocol amendment allowing the continuation of the study after the futility outcome and incorporating the additional analyses requested by the DMC was reviewed by regulatory agencies, IRBs, and investigational sites. These subjects had palovarotene dosing interrupted on or around January 24, 2020. The sponsor allowed dosing to resume as of March 26, 2020, provided each individual site had obtained Ethics Committee approval to do so and the site was able to fulfil regulatory and operational requirements. Subjects were expected to restart dosing over a span of weeks due to these logistical considerations.

2 Overview

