2.2 Study Design

PVO-1A-202 Part C is a Phase 2, multicenter, open-label extension of Study PVO-1A-202 Part B. This continuation of the open-label extension study will give subjects who participated in Part B the opportunity to be followed for up to an additional 36 months. There will be no new subjects in Part C.

Part D annual post last dose of study treatment assessments for up to 2 years will be obtained in subjects who were skeletally immature at the time of study treatment discontinuation in order to obtain longer-term safety data. No new subjects will be enrolled in Part D. Subjects will follow assessments outlined in Table 4 of the protocol as long as they are not 100% skeletally mature. Part C plus Part D total duration will not exceed 48 months.

Added assessments for spinal health will be carried out on low dose WBCT scans collected in the study.

Non Flare-up Based Treatment

Subjects will follow all procedures and undergo all assessments as specified in the Schedule of Assessments in Table 1 and Table 2 of the protocol. Subjects who cannot receive non-flare-up based treatment will only undergo annual assessments (clinical laboratory tests will not be performed). In the event of a flare-up or traumatic event, these subjects will receive flare-up based treatment and undergo all flare-up based assessments, including clinical laboratory tests and radiographs if they have not reached 100% skeletal maturity.

- **Subjects from Part B Continuing Non-Flare-Up Based Treatment into Part C**

Subjects who began non-flare-up based treatment during Part B will continue this visit schedule into Part C and will receive non-flare-up based treatment for up to an additional 48 months. Therefore, these subjects may undergo non-flare-up based treatment for up to 72 months over the entire study. These subjects will follow all procedures and undergo all assessments as specified in the Schedule of Assessments in Table 1 of the protocol, including low dose WBCT scan (excluding head) at all annual site visits (Months 12, 24, 36, 48, 60 and 72). Non-flare-up Day 1 is the first day that non-flare-up based treatment was initiated during Part B, and total duration of treatment will continue into Part C.

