3.2 Part C Study Day, Flare-up Cycle Days and Non-Flare-up Days

3.2.1 Part C Study Day 1

For all subjects, Part C Study Day 1 is defined as the date of informed consent in Part C. Part C Study Day -1 will be the day immediately prior to Part C Study Day 1.

3.2.2 Flare-up Cycle and Flare-Up Cycle Day 1

- A Flare-up Cycle will include the first flare-up and any subsequent intercurrent flare-ups during the same dosing period.
- Flare-Up Cycle Day 1 is defined as the first day that study drug is administered for the first flare-up during that cycle.

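### Part C SAP 5.8 asks for flare-up rates before, during and after the dosing interruption but defines only whole-Part-C follow-up as denominator, so the stated rule gives no valid period rate.

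*SAP*

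**What the plan says.** Part C SAP section 5.8 builds the rate in three steps.

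- The rate: "Rates will be calculated as the total number of flare-ups divided by duration of follow-up (year").
- The denominator: "The duration of follow-up (years) is defined as (last date on study", from which Part C Study Day 1 is subtracted and one day added, the result being divided by 365.25.
- The split: "Flare-up rate will be calculated separately for pre-interruption, during interruption, and after re-start of palovarotene dosing".

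Section 3.2.1 fixes the start of the clock: "For all subjects, Part C Study Day 1 is defined as the date of informed consent in Part C". The clock therefore does not reset when dosing stops or resumes.

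On timing, section 1.2 says of subjects outside the partial clinical hold: "These subjects had palovarotene dosing interrupted on or around January 24, 2020". It adds: "The sponsor allowed dosing to resume as of March 26, 2020", subject to site approvals, with restarts expected to spread over some weeks. Section 2.3 says that children under 14, who stopped from 4 December 2019, would not be put back on treatment. Section 2.2 caps follow-up: "Part C plus Part D total duration will not exceed 48 months".

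**The concern.** A rate for a period needs the events in that period over the time at risk in that period. Section 5.8 defines time at risk once, for the whole of Part C, and then asks for three period rates. A programmer who splits the flare-ups by period and keeps the defined denominator would be following the plan, yet would produce figures governed largely by how long each period lasted.

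This matters because the three figures will be read side by side as flare-up frequency on drug, off drug and on drug again. Section 1.1 says version 1.1 of the SAP was written for the final study report, which covers data from the start of the interruption onward and includes both subjects who restarted and subjects who did not. The split rates fall squarely within that report.

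**Working it through.** The SAP gives no numerical flare-up rate, so there is no figure of its own to reproduce.

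**Is period person-time given elsewhere?** Section 3.1.4 defines a restart baseline for assessments, not time at risk. Section 6.1 gives pause dates for summarizing annualized HO, but no person-time. Section 7.9 defines periods for bone safety data only; its first period runs through February 2020, after dosing had stopped, so it could not serve as the pre-interruption period. Section 5.8 refers to none of these.

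**Inputs from the SAP.** Interruption start about 24 January 2020; earliest permitted restart 26 March 2020. The gap is 7 + 29 + 26 = 62 days, and 62/365.25 = 0.170 year. Maximum Part C plus Part D follow-up is 48 months.

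**Assumptions, not in the SAP.** A constant true rate of 1.5 flare-ups per year (range 0.5 to 3), total follow-up of 4 years (range 3 to 4), and the period lengths shown below.

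**Formula.** With true rate r, period length t and total follow-up T, the expected number of flare-ups in the period is r × t. Dividing by T gives r × t/T. Dividing by t gives r.

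| Assumed case (T = 4 years, r = 1.5) | Before | During | After |
|---|---|---|---|
| 22 + 6 + 20 months | 1.5 × 22/48 = 0.69 | 1.5 × 6/48 = 0.19 | 1.5 × 20/48 = 0.63 |
| 2 years, 62 days, remaining 1.83 years | 1.5 × 2/4 = 0.75 | 1.5 × 0.170/4 = 0.064 | 1.5 × 1.83/4 = 0.686 |
| Never restarts: 1 year, then 3 years off drug | 1.5 × 1/4 = 0.375 | 1.5 × 3/4 = 1.125 | none |
| Any of these, with period person-time | 1.5 | 1.5 | 1.5 (restarters) |

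In each of the first three rows the unrounded entries add to 1.5, the overall rate.

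**Range.** The multiplier t/T does not depend on r. For the interruption it is 0.042 at 62 days, 0.062 at 90 days, 0.123 at 180 days and 0.25 at 365 days with T = 4 years, and 0.057 at 62 days with T = 3 years. In the 62-day, 4-year case, true rates of 0.5, 1, 1.5 and 3 per year would be reported as 0.021, 0.042, 0.064 and 0.127.

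**Can it reverse a real difference?** In the second row, let the off-drug rate truly double to 3 per year. The reported figure is 3 × 0.170/4 = 0.127, still far below 0.75 before and 0.686 after.

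**Fully literal reading.** The numerator is also written without restriction to a period. If neither part is restricted, all three results equal the overall rate, 1.5 in this illustration.

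**The case against.** The best defence is that calculating the rate separately for three periods naturally restricts both numerator and denominator, which would give correct rates. That may well have been the intention. A reader might infer that the plan expressly orders period flare-ups to be divided by total follow-up; it does not, and the scaled rates arise only if the split is applied to the numerator alone. What remains is that the denominator is not left open. It is defined by formula from a fixed start date, and neither way of applying that formula as written gives a valid period rate.

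A reader might also infer that the off-drug period will always look nearly flare-free, so that the drug appears to raise flare-ups. That holds only where the interruption is short relative to follow-up. For subjects who never restart, off-drug time can be long and the distortion can run the other way. The SAP does not give the mix of restarters and non-restarters, so the net direction in a pooled table is unknown.

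Finally, section 5.8 sits under subject data. The flare-up rate is neither the primary endpoint (6.1) nor one of the four listed secondary endpoints (6.2), and section 5.8 plans no test on it. This objection stands and limits the severity.

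**Conclusion.** The point holds: section 5.8 states a denominator that suits the overall Part C rate and is wrong for the three period rates it then requires. Under the numerator-only split, each period rate is multiplied by that period's share of follow-up. For restarters in the illustrations, the interruption rate falls to between 0.042 (62 days) and 0.125 (6 months) of its true value when total follow-up is 4 years. The 22 + 6 + 20 month case creates a false contrast of about 3.7-fold before versus during (0.6875/0.1875) and 3.3-fold after versus during (0.625/0.1875).

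The proportional error follows from the formula alone. The absolute rates and period lengths are assumptions, and the direction depends on restart status. Severity is moderate: a planned descriptive output would be numerically wrong, but no listed endpoint or test is affected.

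**What to change.** Keep the present formula for the overall Part C rate only. For the period rates, define start and end dates for each subject:

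- **Pre-interruption:** Part C Study Day 1 to the day before dosing stopped.
- **Interruption:** the stop date to the day before restart, or to the last date on study for a subject who never restarted.
- **Post-restart:** the restart date to the end of dosing or the last date on study. Report time after final discontinuation, and Part D, separately, since no drug is given then.

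Count flare-ups by onset date within the period and divide by subject-years in that period, including subjects with no flare-ups. Report restarters and non-restarters separately. Keep subjects never treated in Part C, or who stopped before the interruption, out of the interruption and post-restart rates.

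The cost is a paragraph of SAP text and one derivation. It draws on consent, dosing and flare-up onset dates that the SAP already uses in sections 3.2 and 5.9; whether every date is complete cannot be checked from the SAP alone.

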5.9 Compliance

Overall compliance to study drug will be calculated for each subject based on actual study drug taken (mg) and the expected study drug taken (mg) over the course of Part B.

Actual study drug taken will be calculated as the sum of study drug taken from each bottle where study drug taken from each bottle is the number of capsules taken multiplied by capsule strength.

Expected study drug taken will be calculated based on the protocol-defined treatment regimen. Subjects experiencing eligible flare-ups are expected to take 20 mg for 28 days followed by 10 mg for 56 days (or longer if treatment is extended). If the number of days of treatment is extended, weight-adjusted doses, and dose reductions should be taken into account in this calculation. Subjects in the Adult Cohort who are taking non-flare-up treatment are expected to take 5 mg each day they are not taking flare-up based treatment.

For example, if a subject in the Adult Cohort took 90 5-mg capsules from bottle 1, 28 20-mg capsules from bottle 2, and 50 10-mg capsules from bottle 3, then the actual study drug taken is equal to $90 \times 5 + 28 \times 20 + 50 \times 10 = 1510$ mg. The subject started non-flare-up based treatment on Study Day 1, started flare-up based treatment on Study Day 11, and completed Part B on Study Day 174. Treatment was not extended for this flare-up, and doses were not weight-adjusted or reduced. Therefore, the subject was expected to take 20 mg for 28 days followed by 10 mg for 56 days for the flare-up and 5 mg for 90 days (174 total days in Part B – 84 days of flare-up based treatment). Expected study drug taken = $90 \times 5 + 28 \times 20 + 56 \times 10 = 1570$ mg. Compliance would be calculated as: $1510 \text{ mg} / 1570 \text{ mg} = 96.2\%$.

Percent compliance will be summarized for the Treated Population with descriptive statistics. Categories of percent compliance ($<80\%$, $\geq 80\%$) will be summarized for the Treated Population with counts and percentages of subjects.

6 Efficacy Data

Efficacy data for flare-up based treatment assessments will generally be presented by the following treatment groups for the Flare-up Population: PVO 20/10 mg, Prior Non-Flare-up/PVO 20/10 mg, and Combined PVO 20/10 mg. The primary efficacy analysis and other selected efficacy analyses will also be performed using the Flare-up PP Population.

Imaging Reads

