7.1.1 Number of Flare-ups Per Subject-Month

Flare-ups are counted using the number of subject/Investigator-reported flare-ups and AEs with the ‘condition aggravated’ preferred term that are medically reviewed and classified as unique flare-ups (not treated with palovarotene and not recorded as a subject/Investigator-reported flare-up). Rates will be calculated by dividing the total number of flare-ups by the total subject months of follow-up.

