5.10 Compliance

Compliance is defined as (duration of treatment/expected duration of treatment). Calculation of duration of treatment is described in Section 3.2.3 and 3.2.4.

The expected duration of treatment is calculated as following:

- For non-flare-up treatment, expected duration of treatment is calculated as (last non-flare-up dose date – first non-flare-up dose date) – (sum of (all Flare-up cycle dosing periods)) + 1.
- For flare-up treatment, expected duration of treatment is calculated as total of expected flare-up cycle dosing periods across all flare-up cycles. Each expected flare-up cycle dosing period is defined as (last flare-up cycle dose date – first flare-up cycle dose date + 1).

Compliance will be summarized for the Treated Population with descriptive statistics. Compliance in category (<80%, ≥80%) will also be summarized for counts and percentages of subjects.

6 Efficacy Data

Unless otherwise stated, efficacy data will be summarized using Enrolled Population presented by groups: PVO 20/10 mg Only, PVO 5 mg, PVO Total and Never Received PVO Treatment. The PVO 20/10 mg Only group only includes subjects who did not take PVO 5 mg.

Imaging Reads

Imaging data includes results from low-dose WBCT scans (excluding head) and radiographs.

WBCT HO status and total HO volume or new HO volume will be summarized by visit. Those analysis will be included in the interim CSR. All other analysis will be presented in the final CSR.

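### Part C SAP 5.8 asks for flare-up rates in three periods but defines only whole-of-Part-C follow-up as denominator; secondarily, 5.10 compliance ignores early stopping and counts the sponsor's pause as missed dosing

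*SAP*

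**What the plan says.** **Flare-up rate.** Part C SAP section 5.8 gives one formula: "Rates will be calculated as the total number of flare-ups divided by duration of follow-up (year"). It defines the denominator once: "The duration of follow-up (years) is defined as (last date on study – Part C Study Day 1 + 1)/365.25". Section 3.2 fixes the origin: "For all subjects, Part C Study Day 1 is defined as the date of informed consent in Part C". Section 5.8 then closes with the requirement that "Flare-up rate will be calculated separately for pre-interruption, during interruption, and after re-start of palovarotene dosing". It gives no start date, end date or person-time for any of the three periods.

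**Compliance.** Part C SAP section 5.10 defines compliance as duration of treatment over expected duration. For flare-up dosing, "Each expected flare-up cycle dosing period is defined as (last flare-up cycle dose date" minus the first dose date, plus 1). For non-flare-up dosing, the expected duration is likewise the span from first to last dose, less the flare-up cycle dosing periods. The numerators, in sections 3.2.3 and 3.2.4, are the same spans with days not taken or interrupted subtracted. The earlier parts work differently. Part A section 6.10 uses the capsules expected over the planned 42 days. Part B section 5.9 says: "Expected study drug taken will be calculated based on the protocol-defined treatment regimen".

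**The concern.** A rate for a period needs the events and the time at risk from that same period. Section 5.8 supplies only the total time. If a programmer uses the one denominator that is written down, the three results are shares of the overall rate and not three rates. A change across the pause would then partly or wholly reflect how long each period lasted. Readers will naturally use these figures to compare flare-ups on drug, off drug and back on drug.

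For compliance, a denominator that ends at the last dose taken cannot register dosing that should have followed. The table would therefore not show how much of the planned regimen was taken, and could not be set beside the Part A and Part B tables. Conversely, a subject who obeyed the sponsor's instruction to pause and later restarted is scored as having missed those days.

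**Working it through.** **The plan's own figures first.** Part C gives no worked example for either quantity. Those in the earlier parts reproduce:
- Part A section 6.10: 10/42 = 23.8%.
- Part B section 5.9: (90×5 + 28×20 + 50×10) / (90×5 + 28×20 + 56×10) = 1510/1570 = 96.2%.

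**Flare-up rate, inputs.** Section 1.2 dates the general interruption on or around 24 January 2020 and allows dosing to resume from 26 March 2020, so the shortest general pause is about 62 days. Subject-level consent dates and follow-up are not given. I assume Part C starts between October 2017 and July 2018 and total follow-up of 36 to 48 months (1096 to 1461 days).

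**Flare-up rate, formula.** With a constant true rate r, a period of length d has r × d expected flare-ups. Dividing by total follow-up T gives r × d/T. The three literal rates therefore add up to the overall rate r, when each should equal r.

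**Flare-up rate, results for a true rate of 1.00 per year:**
- Start 1 January 2018, 36 months, 62-day pause (753 + 62 + 281 = 1096 days): 753/1096 = 0.69 before, 62/1096 = 0.06 during, 281/1096 = 0.26 after.
- Over all the assumed starts and lengths: 0.39–0.77 before, 0.04–0.06 during, 0.17–0.57 after.
- Understatement in the pause: 1096/62 = 17.7-fold to 1461/62 = 23.6-fold, that is, about 1/18 to 1/24 of the true value.
- Dividing each period by its own time returns 1.00, 1.00 and 1.00.

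**A subject who never restarts.** Assume 20 months before the pause, 28 months after it and a true rate of 2.0 per year. The literal rates are 2.0 × 20/48 = 0.83 before and 2.0 × 28/48 = 1.17 during. Here the pause looks worse although nothing changed.

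**Compliance, formula.** Numerator over denominator reduces to 1 − (missed days)/(first-to-last-dose span, less flare-up days for the non-flare-up ratio). Nothing after the last dose enters.

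**Compliance, flare-up dosing (planned course of 84 days, section 2.3):**
- Last dose on day 20, none missed: 20/20 = 100%; against the planned course, 20/84 = 23.8%.
- Last dose on day 20, 2 days missed: 18/20 = 90.0%, in the ≥80% category.
- Full 84-day course, 17 days missed: 67/84 = 79.8%, in the <80% category.

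**Compliance, non-flare-up dosing (assumed spans, no flare-up days):**
- Restarter, otherwise fully adherent, 62-day pause in 900 days: 838/900 = 93.1%; in 1096 days: 1034/1096 = 94.3%.
- Permanent stop at day 90, none missed: 90/90 = 100%, which ranks above the restarter.

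**The case against.** **Section 5.8 never says that each period is divided by the whole follow-up.** This is true. Calculating a rate separately by period ordinarily means restricting both events and time, and a careful programmer might do so. The defect is a denominator that does not fit the request, not an express instruction to misuse it. But a SAP should not rely on the programmer departing from the only definition it gives. The right inference is not obvious either: section 2.3 says treatment is not restarted in children under 14, and 5.8 does not say when their interruption ends.

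**A reader might infer that the drug-free pause will always look best.** The documents do not support that. It holds, for similar true rates, only where the pause is the shortest period. Section 7.9 describes subjects who did not re-initiate treatment, and for them the pause may be the longest period.

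**A reader might also call it an error that Part C drops a Part B counting rule.** Part B section 7.1.1 adds condition-aggravated adverse events "that are medically reviewed and classified as unique flare-ups (not treated with palovarotene and not recorded as a subject/Investigator-reported flare-up"). That rule belongs to Part B and does not bind Part C. Part C does not limit its count to treated flare-ups, and nothing shows that flare-ups in the pause were recorded only as adverse events. The most that can be said is that Part B and Part C rates use different counting rules and are not directly comparable.

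**Compliance in 5.10 is a coherent measure of adherence while on drug, and early stopping is reported elsewhere.** This largely stands. Sections 5.1, 5.7 and 5.9 tabulate discontinuations and cycle durations, and an early stopper scores exactly 100% only if no earlier day was missed. What remains is that the label suggests more than the ratio measures, that it departs from Parts A and B, and that mandated pause days are charged to restarters. A much larger effect of the pause would need a pause length that the documents do not give.

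**Conclusion.** This should be fixed, but it is not critical. The stated denominator in 5.8 cannot produce the three rates that 5.8 requests. Followed literally, it understates each by period length / total follow-up, unequally, so the before, during and after rates cannot be compared. The 1/18 to 1/24 figure rests on the minimum 62-day pause and on an assumed 36 to 48 months of follow-up. A longer pause gives a smaller understatement, and for non-restarters the direction across periods can reverse.

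The compliance point is secondary. The ratio is valid as on-drug adherence but not as compliance with the planned regimen, and it treats a mandated pause as missed dosing for restarters. With the derivable 62 days that effect is modest (93% on an assumed 900-day span) and stays above the 80% cut.

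Both outputs are descriptive. The flare-up rate is not among the Part C primary or secondary endpoints, and section 4.4 drops formal per-protocol analyses. The 80% cut therefore feeds no efficacy analysis, although section 5.7 still lists a descriptive summary for the Flare-up Per Protocol Population, whose definition uses it.

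**What to change.** **Section 5.8.** Divide the flare-ups with onset in each period by the person-years in that period, with these boundaries:
- Pre-interruption: Part C Study Day 1 to the pause, using the pause dates already in section 6.1.
- Interruption: the pause to restart or, if there is no restart, to the end of study.
- After re-start: restart to the end of study.

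Show flare-up counts and person-years beside each rate, so that the short time at risk in a brief pause is visible. Add a note that Part B and Part C rates count flare-ups differently.

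**Section 5.10.** Take expected flare-up duration from the planned course already in section 2.3, including its extensions and its restarts for intercurrent flare-ups, in line with the planned-regimen approach of Parts A and B. State how stops directed under the SAP's own dosing rules are counted. Exclude sponsor-mandated pause days from expected non-flare-up duration. If the present ratio is kept as well, label it as adherence while on drug.

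**Cost.** SAP wording and re-derivation from existing dates, with no new data. Compliance figures become less favourable for early stoppers.
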